1.1.3 Safety Objective

To compare 2 doses of NTRA-2112 to placebo in preterm infants.

1.2 STUDY ENDPOINTS

1.2.1 Primary Efficacy Endpoint

Numbers of days to achieve full enteral feeding (NFE) is defined as: Number of Days to the first day of achieving enteral feeding of at least 150 ml/kg/day, which must be sustained for at least 3 consecutive days.

For subjects who are marked as fluid restricted, the cut-off value for reaching FEF is 10% less, thus 135 mL/kg/day.

1.2.2 Secondary Efficacy Endpoints

1.2.2.1 Key secondary endpoint:

Number of days to achieve discharge from hospital or readiness for discharge, whichever occurs first.

Readiness for discharge from hospital is defined as achieving all of the below:

- Infant weight ≥ 1800 g
- Stable body temperature
- Capable of oral feeding (reached full enteral feeding and not dependent on PN)

Note: enteral feeding may also include tube feeds.

Confidential Page 10 of 40

1.2.2.2 Other secondary endpoints:

• Growth velocity (g/kg/day) at 6, 8, and 10 days, the last day of treatment (or Day 28), day of discharge, 3-month corrected follow-up, 12-month corrected follow-up, and 24-month corrected follow up

- Change in Z-score at 6, 8 and 10 days, the last day of treatment (or Day 28), day of discharge, 3-month corrected follow-up, 12-month corrected follow-up, and 24-month corrected follow up from initiation of treatment
- Gain in body weight at 6, 8, and 10 days, the last day of treatment (or Day 28), day of discharge, 3-month corrected follow-up, 12-month corrected follow-up, and 24-month corrected follow up
- Number and percentage of infants reaching full enteral feeding within 6, 8, and 10 days from initiation of treatment.
- Total number of days receiving parenteral nutrition
- Number of days to 120Kcal/kg/day
- Number of days to wean-off PN

1.2.3 Exploratory Secondary Efficacy Endpoints

- Number of days to end gastric residuals over 2 ml
- Gain in length during the treatment period and follow up periods (3-month, 12-month, and 24-month corrected gestational age)
- Gain in head circumference during the treatment period and follow up periods (3-month, 12-month, and 24-month corrected gestation age)
- Percent enteral feedings from total nutrition
- Percent parenteral nutrition from total nutrition

1.2.4 Safety Endpoints

- Adverse events (AEs)
- Serious Adverse events (SAEs), including NEC and death
- Blood glucose level
- Complete blood count
- Anti-Insulin antibodies
- Frequency and consistency of stools
- Respiration status
- Lab measures
- Vital signs

Confidential Page 11 of 40

Statistical Analysis Plan V1.3 SAP Date: 06APR2018

1.2.5 Other Endpoints

The first three items below are measured at 24 months corrected follow-up only, the last two items are assessed at 12-month corrected follow-up and 24-month corrected follow-up.

- Bayley scale of infant and toddler development
- Neurodevelopment disability composite
- Child behavior checklist total problem score
- Observer reported outcomes
- Co-morbidities related to Pre-maturity

1.3 SUMMARY OF THE STUDY DESIGN

1.3.1 General Study Design and Plan

[figure not shown]
The study is a multi-center, double-blind, randomized, three-arm, parallel-group, placebo-controlled study to assess the efficacy and safety of NTRA-2112.

Infants will be enrolled within 5 days from birth (at least 6 hours post birth and up to 120 hours post birth) and will be treated for 28 days or until hospital discharge (whichever comes first). The study also includes a follow-up period up to 24 months corrected age.

Full enteral feeding is defined as reaching 3 consecutive days in which the infant consumed at least 150 ml/kg/day of enteral nutrition.

Enrolled infants will be under supervision at a NICU.

[figure not shown]
Figure 1: Study Flow Diagram

Confidential Page 12 of 40

Statistical Analysis Plan V1.3 SAP Date: 06APR2018

Protocol No: FIT-04 Protocol Version: 7.0

Confidential Page 13 of 40

Statistical Analysis Plan V1.3 SAP Date: 06APR2018

1.3.2 Randomization and Blinding

Following screening procedures eligible infants will be randomly assigned to one of the three treatment groups in a 1:1:1 ratio. Randomization, stratified by the gestation age group, should take place as close as possible to treatment initiation and within 24 hours of confirmation of eligibility.

Treatment should commence at postnatal age of up to and including Day 5 (up to 120 hours post birth).

Commencement of the treatment period for infants who are fed solely on own mother's milk should not begin within the first 72 hours post birth.

Randomization will be performed using random allocation generated by computer code. If both members of the twin pair are eligible to be included in the study at the same time, the firstborn will be randomized and the other sibling will be automatically allocated to the same treatment group as the firstborn sibling.

If siblings are determined to be eligible for the study at different times, the sibling who is determined to be eligible for the study first will be randomized first (regardless of birth order), and the other sibling will be automatically allocated to the same treatment group. The assigned medication numbers (kit number) will be entered in the electronic case report form (eCRF), and the corresponding medication kit administered to the infant.

It is assumed that in all cases when twins are both in the study, the first born will be the first one entered, and therefore the one who is randomized. However, to avoid ambiguity, any reference in this SAP to "first born" is intended to mean the first entered (and therefore randomized) into the study. Similarly, reference to "second born" is intended to mean the second twin entered (and who, therefore, is not randomized, but follows the treatment assignment of the twin who was first entered).

In the event that unblinding of treatment allocation is necessary for emergency treatment, it is required that the investigator contact the Medical Monitor for the treatment allocation of the subject. Following discussion on the urgency and requirement for knowing the exact treatment, the Medical Monitor will determine whether to unblind the allocation and provide the treatment assignment to the Investigator (PI). All unblinding events must be reported to the Sponsor and/or Contract Research Organization (CRO) within current approved protocol requirements by the Investigator, study coordinator (other designated study personnel), or by the clinical research associate.

1.3.3 Sample Size and Statistical Power Considerations

Presentation of sample size is based on the hypothesis that NFE in either treatment group is shorter than in the placebo group. Based on limited historical data (Phase 2), the

Confidential Page 14 of 40

conservative mean is 8.0 days for the placebo group and 6.6 days for each of the 2 active dose groups. This assumes a standard deviation of 3.5 days for each group.

The analysis will be based on a nonparametric test. The NFEs for each infant in the FAS will be ranked from shortest time (the best outcome) to longest time. Infants who do not achieve full enteral feeding and also experience necrotizing enterocolitis (NEC) will be assigned the next set of ranks; all the infants experiencing NEC will be ranked in terms of their time to NEC (the earlier the worse) and will be assigned ranks one greater than the rank of the longest time to achieve NFEs. All infants who do not achieve full enteral feeding and die will be assigned the next set of ranks, again with the earliest deaths assigned the largest (i.e. worst) rank. Thus, each infant who has achieved EN or who has died or suffered NEC will have a recorded rank.

Randomization will be stratified by center and by gestational age group. The statistical analysis will stratify the infants by gestational age group and region (North America, Europe, and Israel), but not by center. Because the analysis will be based on ranks, a van Elteren test will be used to compare NTRA-2112 to placebo. To calculate sample size, an independent groups t-test for 85% power to account for the reduced power of the non-parametric test was used (i.e., expect that a t-test with 85% power to have at least 80% power when the van Elteren test is applied). A two-side 5% test will be used to compare each active dose to placebo. These calculations give N = 115 infants per group. To account for the reduction in power caused by potential missing data, the sample size was increased to 130 per group or a total sample size of 390

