2.2.1.4 Sensitivity Analysis: Missing Values

Some infants in the FAS are expected to drop out of the study or, for some other reason, not to have a ranking. As described in Section 2.2.1.3, multiple imputation will be used to include these infants in the analysis of the primary and key secondary endpoint.

The following sensitivity analyses will be conducted on the primary and key secondary endpoint to explore the effect of these missing values:

- Worst reasonable case analysis: Infants in an NTRA-2112 group with a missing rank will be assigned the median rank in the placebo group and infants in the placebo group with a missing rank will be assigned the median rank in the combined NTRA-2112 groups. The van Elteren test, stratified by gestation age group and region (North America, Europe, and Israel) will be performed.
- **Best reasonable case analysis**: Infants in an NTRA-2112 group with a missing rank will be assigned the median rank in the respective NTRA-2112 group and infants in the placebo group with a missing rank will be assigned the median rank in the

Confidential Page 25 of 40

placebo group. The van Elteren test, stratified by gestation age group and region (North America, Europe, and Israel) will be performed.

Tipping point analysis: Infants in either of the NTRA-2112 groups with a missing rank will be assigned varying ranks to find the point at which statistical significance is lost. Specifically, if the outcome of the hypothesis test is in favor of a NTRA-2112 group over the placebo group (P-value <0.05), then one day will be added to each of the imputed values for the NTRA-2112 group in each copy of the imputed dataset, whilst the data for the placebo group will remain the same. The 5 imputed datasets will then be combined to run the van Elteren test results using PROC MI procedure in SAS. This "day shifting" will be repeated with one extra day at a time until the outcome of the hypothesis test is no longer in favor of the NTRA-2112 group over the placebo group (i.e. the P-value becomes greater than 0.05). As the overall ranks of NTRA-2112 group increase as the results of adding one day each time to each imputed missing rank, the highest rank for the imputed missing ranks will be truncated at Day 30 (implying that a missing data point is as bad as a death).

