2.2.1.7 Sensitivity Analysis: Breaking Tied NFE Rankings

For the infants who have the same NFE value which lead to the tied NFE rankings, their baseline enteral feeding volume will be used to break the tie. Specifically, the infant with the lowest baseline enteral feeding volume will be ranked lowest among them, the infant with the second lowest enteral feeding volume will be ranked the second lowest, and so on. For infants who have the same NFE rank and the same baseline enteral feeding volume, their NFE ranks will remain to be tied. For subjects who have unique NFE rankings, they will retain their ranks if there were no ties. For infants who experience NEC (Necrotizing Enterocolitis) and infants who die, their NFE will be assigned to Day 29 and Day 30 without breaking ties by their baseline enteral feeding volume. The individual ranks among subjects experiencing NEC and the individual ranks among subjects who die will be handled according to Section 1.3.3. For subjects who didn't meet the enteral feeding criterion during the treatment period, their NFE will be censored on Day 28 without breaking by their baseline enteral feeding volume. The testing of such NFE ranking will be analyzed in the same way as described in 2.2.1.1 for the van Elteren test, stratified by gestational age group and region (North America, Europe, and Israel).

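### The visible SAP ranking rules give no primary-endpoint rank to an infant observed alive and NEC-free to Day 28 without full feeding, and other sections conflict on whether that infant is imputed or scored at Day 28.

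*SAP*

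**What the plan says.** - **Ranking rule.** SAP 1.3.3 orders the feeding times (NFE) from shortest to longest. Infants with NEC who never reached full feeding come immediately after the longest achieved time, and deaths without full feeding come last. It ends: "Thus, each infant who has achieved EN or who has died or suffered NEC will have a recorded rank". Protocol 12.3 has the same three groups.
- **Scores.** SAP 2.2.1.3.2 adds Day 29 for NEC and Day 30 for death (181 and 182 for the discharge endpoint, NRD). SAP 2.2.1.1 adds nothing for other infants.
- **Infants without a rank.** SAP 2.2.1.4 refers to infants who drop out and to those who lack a ranking on any other ground, and says that "multiple imputation will be used to include these infants in the analysis of the primary and key secondary endpoint". Protocol 12.4.5 likewise imputes any missing rank.
- **Narrower description.** SAP 3.1, on the interim analysis, describes the imputation as dealing with values lost through drop-out, with a trigger based on early termination other than NEC or death.
- **Tie-breaking check.** For infants who did not meet the feeding criterion in the treatment period, SAP 2.2.1.7 says "their NFE will be censored on Day 28 without breaking by their baseline enteral feeding volume".
- **Not visible.** The text of SAP 2.2.1.3.1, to which 3.1 refers for the imputation, is not in this copy.

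**The concern.** An infant observed through Day 28 without full feeding is not missing data. The feeding time is known to be longer than the window, and such infants are the clearest treatment failures for a malabsorption endpoint. If they are imputed from infants who did reach full feeding, a known failure receives a typical feeding time and any between-arm difference in failure rate drops out of the primary test. The error can run either way: it can hide an excess of failures on an active dose or discard a real reduction.

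The conflict also affects 2.2.1.7. If the primary analysis imputes these infants and the tie-breaking analysis puts them at Day 28, the two differ in more than the ties, and a change in the result could not be attributed to tie-breaking.

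**Working it through.** **1. Where the infant falls.**

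| SAP section | Alive, NEC-free, no full feeding at Day 28 |
|---|---|
| 1.3.3 | no tier; NEC follows the longest achieved time directly |
| 2.2.1.3.2 | no score; 29 and 30 are for NEC and death only |
| 2.2.1.4 | has no rank, so imputed |
| 3.1 | neither dropped out nor terminated early, so not imputed |
| 2.2.1.7 | Day 28 |

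If 2.2.1.4 governs, a known outcome is imputed. If 3.1 governs, the infant is neither ranked nor imputed by any visible primary rule. Either way the text needs repair.

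**2. The plan's own figure.** The inputs come from SAP 1.3.3. Each dose is tested against placebo at a two-sided 5% level. On power, the SAP says "an independent groups t-test for 85% power to account for the reduced power of the non-parametric test was used". The SD is taken as 3.5 in every arm. The effect is a difference of 8.0 − 6.6 = 1.4 days, from this statement: "conservative mean is 8.0 days for the placebo group and 6.6 days for each of the 2 active dose groups". Allocation is equal (SAP 1.3.2). Then

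n = 2(z₀.₉₇₅ + z₀.₈₅)²σ²/δ² = 2 × (1.960 + 1.036)² × 3.5²/1.4² = 2 × 8.976 × 6.25 = 112.2, so 113 per group.

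The exact t-test gives 113.2, so 114. The SAP states 115, so the figure reproduces. Raising 115 to 130 allows for 1 − 115/130 = 11.5% missing.

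**3. How many such infants the planning figures imply.** Under SAP 1.2.1, NFE is the first of three qualifying days, so the latest value observable in 28 days is Day 26. With mean 8.0 and SD 3.5 (placebo), P(NFE > 26) is about 1 × 10⁻⁷ (normal), 0.03% (gamma) or 0.12% (lognormal). The largest gives 130 × 0.0012 ≈ 0.16 infant. With SD 5.0, a value considered in SAP 3.1, the range is 0.02% to 1.0%, and the largest gives 130 × 0.0097 ≈ 1.3 infants.

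**4. Effect on the test if there are more.** The failure shares below are assumptions; the documents give none. Set-up: 130 per arm, gamma NFE in whole days with the SAP means and SD, tie-corrected Wilcoxon without strata standing in for van Elteren, and 3,000 runs. Failures are either scored at Day 28 or imputed five times from achievers in the same arm. Entries are the chance of a significant benefit.

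| Failures, placebo / active | Day 28 | Imputed |
|---|---|---|
| 0% / 0% | 93% | 93% |
| 2% / 2% | 92% | 93% |
| 5% / 5% | 88% | 92% |
| 10% / 10% | 79% | 91% |
| 5% / 2% | 96% | 93% |
| 2% / 5% | 80% | 93% |
| 10% / 5% | 96% | 92% |
| 5% / 10% | 62% | 92% |
| 2% / 10% | 47% | 91% |

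A second simulation (4,000 runs, imputation approximated by leaving failures out) gives 75% v 93% at 2% placebo and 6% active, and 97% v 93% with the shares reversed. With a drug mean of 6.9 and failures of 10% placebo and 4% active, it gives 90% v 75%.

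With an expected one failure in one arm only (1/130 = 0.77%), the two rules give 92% v 94% if that arm is active and 95% v 93% if it is placebo. With 1% in both arms they give 93% v 93%.

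The imputed column hardly moves with the failure shares: under that rule the test does not see failures.

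**The case against.** The strongest reply is that Day 28 is already intended. NEC at 29 and death at 30 leave a slot at 28, just beyond the last observable time of Day 26. Section 2.2.1.7 lists 28, 29 and 30 together, and NRD follows the same pattern: observation to 180 days (SAP 4), then 181 and 182. SAP 3.1 confines imputation to drop-out. The section that governs imputation is missing from this copy, and that cannot be held against the plan. On the planning figures such infants are very rare.

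Much of this stands. A reader might infer that the SAP does impute known failures as successes. The documents do not establish that: it requires that 2.2.1.3.1 covers infants who completed the window, and that its model allows values better than Day 28. Nor can it be said that 2.2.1.7 puts early dropouts at Day 28. Its wording can be read that way, but also as meaning only infants observed throughout.

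Three things remain.

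- The intended slot is not written into 1.3.3, which runs NEC on directly from the longest achieved time, and the wording of 2.2.1.4 is broader than drop-out.
- Rarity is not assured. The tail figures describe a distribution of achieved times. Protocol 5.1 reports that the Phase II study required at least 750 g; this trial enrols from 500 g, and protocol 12.1.1 itself calls the Phase II population narrower.
- Other analyses would help to reveal a difference in failures: counts in 2.2.1.8, proportions by Days 6, 8 and 10 in 2.2.2, and the log-rank and tipping-point analyses in 2.2.1.4. None alters the primary test. The worst and best reasonable case analyses would give an unranked failure a group median, so neither treats it as a failure.

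**Conclusion.** The point holds as a conflict in the visible text. SAP 1.3.3 and 2.2.1.3.2 omit this infant; 2.2.1.4 with protocol 12.4.5 would impute a known outcome; 3.1 and 2.2.1.7 point elsewhere. Whether imputation would actually occur is open, because 2.2.1.3.1 is not visible and may already fix Day 28. If it does, 1.3.3 and 2.2.1.4 should be aligned with it.

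The size depends on an unknown rate. At about one infant per arm or fewer, the choice moves the chance of a significant benefit by about two percentage points at most. If failure rates differ by several points it is material: about 75% v 93% under the assumed 2% on placebo and 6% on drug. These figures are illustrative. They rest on assumed shares, a gamma distribution, an unstratified test without NEC or deaths, and imputation from achievers. They should not be read as an estimate of bias in this trial. The point is worth settling before unblinding because the rule decides how observed failures count in the primary test.

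**What to change.** 1. In SAP 1.3.3 and 2.2.1.3.2, add a tier: infants observed to Day 28, alive and NEC-free, without full feeding share one tied rank, after every observed NFE and before NEC. Use Day 28 for NFE and the analogous Day 180 tier for NRD.
2. In SAP 2.2.1.4, limit multiple imputation to infants whose follow-up ended before full feeding, NEC, death or the end of the window. Align 2.2.1.3.1 and 3.1 with this.
3. Use the same split in 2.2.1.7, so that it differs from the primary analysis only in breaking ties.

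The cost is SAP wording and programming before unblinding. No new data are needed and the stated sample size is unchanged. One consequence should be acknowledged: if failures are equally common in both arms, the added tier lowers power (88% at 5% each and 79% at 10% each in the simulation above, against 93% with none).

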1.4 GENERAL CONSIDERATIONS

All descriptive statistics for continuous variables will be reported using mean, standard deviation (SD), median, minimum and maximum. Categorical variables will be summarized as number (percent) of subjects.

Confidence intervals (CIs) will be 95% and all tests will be two-sided, unless otherwise specified in the description of the analyses.

P-values will be rounded to three decimal places. If a P-value is less than 0.001 it will be reported as "<0.001." If a P-value is greater than 0.999 it will be reported as ">0.999."

For both fraternal and identical twins eligible for the study, the primary analysis will include only the first-twin (and only twin) to be randomized. If only one twin is eligible, then that twin (whether first to be randomized or second) will be included in the primary analysis. The same approach will be applied to the key secondary endpoint, the other secondary endpoints, the exploratory secondary endpoints, the other endpoints, and the analyses of the primary and key secondary endpoints on per protocol set, unless specifically specified which twin(s) will be included.

Confidential Page 15 of 40

Statistical Analysis Plan V1.3 SAP Date: 06APR2018

1.5 DEFINITIONS OF ANALYSIS SET

1.5.1 Full Analysis Set (Intention-to-treat)

The FAS will consist of all randomized singletons and, for twins who both participate in the study, both will be included.

In the situation where both twins are included in FAS, whether only the first twin to be randomized, or the second twin assigned to the same treatment group as the first randomized twin, or the both twins who will be included in the efficacy analyses on FAS will be explicitly stated in Section 2.2.

1.5.2 Per-Protocol Analysis Set

Per- protocol (PP) set consists of subjects in FAS who do not have an important protocol deviation. The categories of the importance protocol deviation that are thought to have a major impact on the interpretability of the overall interpretation of safety and efficacy of the trial are provided in Section 2.1.2.

The approach described in the protocol of using methods that separate the reasons for noncompliance from the effect of study drug (e.g. Robins, 1989) will not be followed. Instead, the more common approach of defining a PP set based on study compliance will be adopted. This is not considered as a major change although it will be mentioned in Section 4.0 – Summary of Major Changes in the Planned Analyses.

1.5.3 Safety Analysis Set

The safety analysis set will consist of all infants in whom any study drug (placebo or NTRA-2112) was initiated. If both members of a pair of twins are participating in the study, the safety analysis set will include both infants.

